STUDY PROTOCOL, INCLUDING STATISTICAL ANALYSIS PLAN (SAP)

Official Title: Nurse-to-Family Telehealth for Pediatric Transfers: A Randomized Controlled Pilot Trial

ClinicalTrials.gov NCT Number: NCT05593900.

- First Posted: October 26, 2022
- Last Update Posted: December 5, 2022

Protocol Document Date: October 23, 2022

Principal Investigator: [name], MAS

Institution: University of California Davis

Funding Sources:

- Eunice Kennedy Shriver National Institute of Child Health and Human Development, National Institutes of Health (NIH) (K23HD101550 and supplement K23HD101550-03S1 to [name])
- The Doris Duke Charitable Foundation COVID-19 Fund to Retain Clinical Scientists awarded to UC Davis School of Medicine by the Burroughs Wellcome Fund

IRB Approval: University of California Davis Institutional Review Board, approved 2/1/2018

Objectives

Our central hypothesis is that telehealth use to connect a care team member from the receiving hospital virtually with the child's parents may increase family-centeredness of care, reduce parent stress, and improve triage appropriateness. A pilot study is needed to explore the feasibility of conducting a nurse-to-family telehealth trial. We therefore aim to test the feasibility of conducting a parallel cluster randomized trial comparing nurse-to-family telehealth communication to usual care for pediatric transfers. Feasibility will be assessed by protocol assignment adherence, fidelity, and survey response rates.

Eligibility

Inclusion: Eligible patients will be children aged eight days to less than or equal to 18 years who present to a participating community hospital emergency department (ED), are accepted for inter-facility transfer, are assigned to arrive as a direct admission (i.e., ED-to-inpatient) to one of three eligible hospital units, and have an adult parent or guardian at the bedside with English language preference. The eligible units include the pediatric intensive care unit (ICU) and two pediatric acute care units.

Exclusion: Transfer consultations for children less than 8 days of age and those destined for the neonatal ICU will be excluded, since neonatal patients have unique transfer patterns. Children who are transferred from ED-to-ED will be excluded to prioritize feasibility and first test the intervention in a homogeneous context. This trial excludes those who do not have a parent with English language preference, because we will use an existing telehealth platform that is only available in English. We will first pilot test this intervention before adapting the platform's family-facing interface into additional languages.

All eligible children will be enrolled in the study. This research has a waiver of consent for the intervention, because telehealth visits are an existing clinical resource that can be used for all transferring patients. The decision to use telehealth in this trial will be encouraged in the intervention arm but will remain optional; no nurse or parent will be required to use telehealth. The parent survey that will be used for data collection of exploratory outcomes will have elements of informed consent before the survey questions.

Exploratory Outcomes

In addition to testing feasibility objectives (Table 1), we will measure subject-level exploratory outcomes data to test feasibility of data collection and to obtain effect size estimates. Exploratory outcomes include family-centered care, family experience, parent acute stress, parent distress, and change in level of care. Family-centered care of the community ED encounter will be assessed using the ED Family-Centered Care Experience (ED-FACCE) survey. Family experience will be measured using the two items measuring overall experience from the ED Consumer Assessment of Healthcare Providers and Systems (CAHPS) survey. Parent acute stress and distress will be assessed using the Emotional Distress: Anxiety measure. Change in level of care will be measured at two timepoints: (1) between initial unit assignment and post-transfer arrival and (2) between post-transfer arrival until 12 hours after arrival. Change in level of care will be defined as switching from an acute care unit or service to an intensive care unit or service, and vice versa.

Table 1: Feasibility objectives

Feasibility objective	Indicator	Criteria for success
(1) Protocol assignment adherence	Proportion of eligible patients for whom the protocol assignment (telehealth initiated versus usual care) is followed	Adherence will be 75% or greater
(2) Fidelity: timing of delivery	Whether the telehealth connection is initiated prior to the patients' arrival to the children's hospital	Fidelity will be 75% or greater
(3) Survey response rate	Survey response rates for each survey-derived outcome	Survey response rates will be 75% or greater

Procedures Involved

Randomization: The unit of randomization will be the community hospital, which decreases contamination in comparison to randomization at the patient level (under which each ED would have simultaneous telehealth visits and usual care). We will use constrained randomization to better balance the intervention and control arms with respect to ED-to-children's hospital distance and pediatric transfer volume. Distance will be categorized into less than 21 miles, 21-50 miles, and more than 50 miles. Transfer volume will be categorized into less than 21, 21-60, and more than 60 annual pediatric transfers that arrive as direct admissions to a pediatric ICU or pediatric acute care unit.

Intervention: Per standard procedures, after a children's hospital physician accepts a patient for transfer, the transferring patient is assigned a hospital unit by the bed control nurse. The charge nurse will accept or deny the patient to their unit. Upon accepting a patient to their unit, this charge nurse will determine whether the transferring patient meets trial eligibility criteria and is transferring from an intervention-arm ED site. Upon confirmation that the patient is eligible to receive a nurse-to-family telehealth visit, the charge nurse will call by telephone the community hospital ED and ask the bedside nurse to offer a telehealth visit to the patient's parent(s). If the parents would like to have a nurse-to-family telehealth visit, the ED nurse will give the parent's cell phone number or email address to the children's hospital charge nurse.

The children's hospital charge nurse will then use their video-enabled computer to launch a telehealth visit using the secure telehealth application called ExtendedCare. The ExtendedCare platform meets Health Insurance Portability and Accountability Act security rules and launches from the patient's electronic health record. From within this telehealth visit, the charge nurse will send an electronic message (e.g. via text or email) to the parent and wait for the parent to join the visit (establish a secure videoconference). The message to the parent includes a link that can be clicked to open a browser that allows the parent to join the telehealth visit. The parent does not need to download or use any application or program.

Charge nurses are instructed to initiate the telehealth visit prior to the patient leaving the community hospital ED and to wait at least five minutes for the parent to join the telehealth connection. Charge nurses are also instructed that the content of the discussion during the visit is intended to prepare the family and charge nurse for the transfer process and the patient's arrival. This workflow requires that the parent has a smart phone with access to text messaging or email. If a parent does not have a smart phone with access to text or email but would like to speak with the charge nurse, a phone call will be offered instead. Other interventions related to parent-provider communication that are delivered prior to the arrival at the post-transfer hospital will be prohibited during the trial.

Control: Subjects presenting to control-arm ED sites will receive usual care. These subjects will transfer to the children's hospital without the parent communicating with the charge nurse. The charge nurse will not have direct communication with anyone from the ED. The charge nurse will communicate with the children's hospital bed control nurse and review the written documentation about the patient in the electronic health record.

Data collection: Data collection for the feasibility objectives and exploratory outcomes will include chart review of the electronic health record and parent surveys. Parent surveys will be distributed to one parent per enrolled patient. Parent respondents will include only English-proficient individuals who were with their child during the ED visit. For children who had more than one parent at their ED bedside, we will let the parents select the single respondent. Eligible parents will receive the family-centered care, experience, and anxiety instruments 0-3 days after the ED encounter. Parent distress will be measured at 30 days from the ED encounter. Surveys not completed within 21 days of distribution will be considered non-response. Participants will receive a \$25 gift card for each survey packet that they return. Parents completing both survey packets will therefore receive a total of \$50 in gift cards.

Data collection for the exploratory outcome change in level of care will use chart review. Electronic health record data will be used to abstract patient demographics (age, race, ethnicity, sex, insurance, California Healthy Places Index) and utilization variables (admitting service, length of stay, disposition). Demographic characteristics of family caregivers (age, race, ethnicity, gender, education, smart phone access, digital literacy score) will be collected in the survey packets.

STATISTICAL ANALYSIS PLAN (SAP)

For feasibility objectives, proportions with 95% CI will be calculated for protocol assignment adherence, fidelity, and survey response rates to determine if each of the feasibility objectives is met. For the exploratory

outcomes, analyses will be descriptive, designed to provide effect size estimates with 95% CI. To account for the cluster randomized design, we will use analysis methods for clustered data when estimating confidence intervals, treating ED sites as clusters.

Although we do not anticipate strong cluster effects for the feasibility objective outcomes, we recognize that our confidence intervals will be inflated both by the modest intracluster correlation and by the use of critical values from t-distributions with only 5 or 2 degrees of freedom, depending on whether the objective concerns patients from all 6 sites (objectives 1 and 3) or from just the 3 intervention sites (objective 2). Hence, we anticipate that our actual sample size will perform as effectively as a sample size one half smaller for objectives 1 and 3 and as 60% smaller for objective 2. For feasibility outcomes, an actual sample size of 120 will be sufficient to estimate proportions with error margins (i.e., half-width of 95% CI) of ≤ 12.7 percentage points for the primary feasibility objective (objective 1) and for objective 3, which involve the full sample. For objective 2, we anticipate fidelity testing on an actual sample of size 45, which will result in error margins no greater than 23.0 percentage points. This pilot trial is not powered to determine the relative benefit of telehealth versus usual care, as that important question will be answered in a future efficacy trial. The chosen sample size of 120 patient encounters prioritizes feasibility over power.

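### Objective 1 pools adherence over both arms under one 75% criterion, so high control-arm adherence can offset weak telehealth delivery in the intervention arm

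*Combined protocol and SAP*

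**What the plan says.** Table 1, objective (1), sets the indicator as "Proportion of eligible patients for whom the protocol assignment (telehealth initiated versus usual care) is followed" and the criterion as "Adherence will be 75% or greater". A patient counts as adherent if telehealth was initiated at an intervention site or if usual care was given at a control site.

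The SAP's precision paragraph confirms the pooling. It separates the objectives by whether they draw on all 6 sites (objectives 1 and 3) or on the 3 intervention sites (objective 2), names objective 1 as the primary feasibility objective, and bases its margin on all 120 patients. It gives no adherence estimate or criterion for either arm alone.

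On the decision, the SAP says that proportions with 95% CIs will be calculated "to determine if each of the feasibility objectives is met", with confidence intervals estimated "treating ED sites as clusters". It does not say whether the point estimate or a confidence limit is compared with 75%.

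Objective 2 asks whether the connection was initiated before arrival, also with a 75% criterion. The SAP adds: "For objective 2, we anticipate fidelity testing on an actual sample of size 45". It does not say who those 45 are.

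**The concern.** The two halves of the pooled proportion carry different information. Under Procedures Involved, adherence at an intervention site needs a chain of steps: the charge nurse recognises an eligible patient from an intervention site and telephones the ED, the bedside nurse offers a visit, the parent accepts and gives contact details, and the charge nurse launches the visit. The Eligibility section makes use of telehealth optional for nurses and parents. Adherence at a control site needs only that none of this happens.

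Control adherence may therefore be high by default and lift the pooled figure while delivery in the intervention arm is poor. The pooled figure also hides which problem occurred. With equal arms, 60% initiation with 100% control adherence gives 80%, and so does 90% initiation with 70% control adherence. The first is under-delivery and the second is contamination, and they call for different remedies before the efficacy trial that the SAP foresees.

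**Working it through.** **Inputs from the documents.** N = 120; 6 sites, 3 of them intervention sites; criterion 75%; an effective sample one half smaller for objective 1 and 60% smaller for objective 2; margins of 12.7 and 23.0 points.

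**Assumptions.** 60 patients per arm (20 per site), because arm sizes are not stated. Control adherence of 80-100%, because no figure is given.

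**The plan's own figures.** The effective n for objective 1 is 120 × 0.5 = 60, and 1.96 × √(0.25/60) = 0.127, which matches 12.7. For objective 2 it is 45 × 0.4 = 18, and 1.96 × √(0.25/18) = 0.231, which agrees with 23.0 apart from rounding.

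**Point-estimate rule.** Success needs 0.75 × 120 = 90 adherent patients. With pI the initiation proportion, pC the control adherence, and nI and nC the arm sizes, the break-even is pI = (90 − nC × pC)/nI. The last column is the chance of reaching 90 when true initiation is 60%, from the sum of Bin(60, 0.60) and Bin(60, pC) without clustering.

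| Control adherence | Break-even initiation | Chance objective 1 is met at true initiation of 60% |
|---|---|---|
| 100% | 30/60 = 50% | 0.96 |
| 95% | 33/60 = 55% | 0.80 |
| 90% | 36/60 = 60% | 0.55 |
| 85% | 39/60 = 65% | 0.30 |
| 80% | 42/60 = 70% | 0.13 |

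At 100% control adherence, beta-binomial simulation (3 intervention sites of 20) lowers 0.96 to 0.94, 0.89 and 0.84 for ICCs of 0.01, 0.05 and 0.10.

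**Arm split.** At 100% control adherence, 50 intervention and 70 control patients give (90 − 70)/50 = 40%; 70 and 50 give (90 − 50)/70 = 57%.

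**Lower-limit rule, two constructions.**

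- *Wald, effective n of 60.* Solving P − 1.96 × √(P(1 − P)/60) = 0.75 gives a pooled P of about 84.2%. With equal arms pI = 2P − pC, so initiation must be about 68%, 73% or 78% at control adherence of 100%, 95% or 90%.
- *t interval on six site proportions, 5 df, sites taken as identical within arm.* The margin is 2.571 × SD/√6. Three sites at 0.60 and three at 1.00 have mean 0.80 and SD 0.219, so the margin is 0.230 and the lower limit 0.57. Setting the limit to 0.75 gives initiation of 76.7%, 76.4% or 76.0% at control adherence of 100%, 95% or 90%.

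The second construction counts the gap between arms as variation among sites, which is why it is stricter at high control adherence.

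**Criterion on the intervention arm alone.** With 60 patients, 75% is 45/60. As a point-estimate rule, P(Bin(60, p) ≥ 45) is 0.01, 0.57 and 0.99 at true initiation of 60%, 75% and 85%; with an ICC of 0.10 it is 0.09, 0.56 and 0.90. Using the plan's 60% loss for three sites, the effective n is 60 × 0.4 = 24 and the worst-case margin is 1.96 × √(0.25/24) = 0.200.

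**The case against.** **The pooled figure fits the aim.** The Objectives section states: "We therefore aim to test the feasibility of conducting a parallel cluster randomized trial". Adherence to assignment in both arms is a sensible measure of that. This stands, and the pooled figure should be kept.

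**The harm rests on unstated conditions.** It needs a point-estimate decision and high control adherence, and its size depends on the arm split. At 80% control adherence the break-even is 70% and little is hidden. High control adherence is not assured, because the same three receiving units serve both arms and telehealth is available for every transfer. The SAP's reference to "critical values from t-distributions with only 5 or 2 degrees of freedom" may mean that the interval plays a part in the decision. All of this stands as a limit on size. Yet the wording of the criterion reads most naturally as a point estimate, and nothing in the SAP says otherwise.

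**Objective 2 may already do the work.** Over all intervention-site patients, a patient with no visit initiated fails objective 2, so initiation of 50-60% would fail it. That is a possible reading. But 45 is also 75% of an assumed 60, which would suit a denominator of initiated visits only, and low initiation could not then fail the objective. The documents settle neither reading.

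**Consequences are limited.** No progression rule depends on objective 1, arm-level adherence can be derived from the data, and the interval would be wide. This stands.

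**Conclusion.** The point holds and is worth fixing. Under a point-estimate rule with 60 per arm, the primary feasibility objective can be reported as met although 40-50% of eligible intervention-arm families had no visit initiated, provided control adherence is 90-100% and correspondingly high. Confidence is medium, because arm sizes, control adherence and the decision rule are all assumed.

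Three stronger readings are tempting but unsupported.

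- A reader might infer that any initiation of 50-60% passes with any control adherence of 90-100%. It does not: 50% with 90% gives 70%, and 50% with 95% gives 72.5%.
- A reader might infer that a lower-limit rule either removes the masking or leaves it untouched. The SAP names no interval method, and the answer depends on it. With the Wald limit and 100% control adherence, initiation about 7 points below 75% still passes; with the six-site t interval, or at 90% control adherence, none does.
- A reader might infer that a poorly delivered intervention would go forward to the efficacy trial on this result, or that delivery could not be recovered from the data. The plan ties no progression decision to objective 1, and adherence by arm can be tabulated. The risk is a misleading headline on the primary objective.

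**What to change.** In Table 1 and the SAP:

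1. Report adherence separately by arm with clustered CIs.
2. Apply the existing 75% criterion to intervention-arm initiation, that is, telehealth initiated divided by all eligible intervention-arm patients.
3. Report control-arm adherence as the measure of contamination, and keep the pooled figure with its clustered CI as a measure of trial conduct.
4. State whether the point estimate or a confidence limit is compared with 75%.
5. State objective 2's denominator.

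These are text edits and need no new data. The costs are a harder target and less precision. On a point-estimate rule, 45/60 is reached only about 57% of the time when true initiation is 75%. The worst-case margin becomes about 20 points instead of 12.7, and that is a planning approximation: with a t critical value of 4.303 on 2 df and no clustering at all, 4.303 × √(0.25/60) gives 27.8 points.

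The choice in item 4 belongs to the sponsor but has consequences. A Wald lower limit on this arm alone, with effective n of 24, would need 53/60 (88%; lower limit 0.755, against 0.731 for 52/60), so it should not be adopted by default.

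Optionally, count separately the intervention-arm patients whose parents declined or were offered a phone call, so that optional use is not read as failure of the workflow. This may need one log field if chart review does not show it.

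### Does the 21-day return rule undermine the acute-stress outcome by accepting scores completed close to the 30-day distress measurement?

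*Combined protocol and SAP*

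**What the plan says.** The Exploratory Outcomes section lists the two constructs separately: "Exploratory outcomes include family-centered care, family experience, parent acute stress, parent distress, and change in level of care". It gives them one instrument: "Parent acute stress and distress will be assessed using the Emotional Distress: Anxiety measure". The stated purpose is that "we will measure subject-level exploratory outcomes data to test feasibility of data collection and to obtain effect size estimates".

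The Data collection paragraph under Procedures Involved sets the timing. For the first packet: "Eligible parents will receive the family-centered care, experience, and anxiety instruments 0-3 days after the ED encounter". For the later construct: "Parent distress will be measured at 30 days from the ED encounter". A single return limit follows, written for surveys in general and counted from distribution: "Surveys not completed within 21 days of distribution will be considered non-response".

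In Table 1, the indicator for objective 3 is "Survey response rates for each survey-derived outcome" and the criterion is "Survey response rates will be 75% or greater". The SAP plans proportions with 95% confidence intervals for the feasibility objectives and descriptive effect sizes with 95% confidence intervals for the exploratory outcomes. It says nothing about completion date.

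**The concern.** In these documents, timing is the only visible difference between acute stress and distress, because the instrument is the same. A return limit of three weeks looks long for something labelled acute. A parent who answers on the last permitted day is much closer to the 30-day measurement than to the ED encounter, yet that score enters the acute-stress analysis and counts toward the 75% criterion.

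Two things would be at stake. The pilot could declare collection of acute stress feasible although many scores came late, and so misinform the planning of the later efficacy trial. The acute-stress effect estimate could also mix early and later states and be pulled toward whatever effect remains weeks afterwards.

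**Working it through.** **The plan's own figure.** For objectives 1 and 3 the SAP takes 120 encounters to perform like half that number, so the effective size is 60. The worst-case half-width is 1.96 × √(0.25/60) = 0.1265, or 12.65 points. This reproduces the stated bound of 12.7.

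**Dates.** The inputs are distribution on day 0-3, a limit of 21 days from distribution, and distress at day 30, all from the Data collection paragraph.

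| Sent on day | Last accepted day | Days before day 30 |
|---|---|---|
| 0 | 0 + 21 = 21 | 9 |
| 1 | 1 + 21 = 22 | 8 |
| 2 | 2 + 21 = 23 | 7 |
| 3 | 3 + 21 = 24 | 6 |

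The gap of 6-9 days is thus correct, but it is a worst case measured to a nominal date. The same limit covers the second packet. If that packet is sent on day 30 (an assumption, since its send date is not given), it is accepted until 30 + 21 = day 51. The distance between the two completions then runs from 30 − 24 = 6 days to 51 − 0 = 51 days.

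**Does following the plan give a wrong result for objective 3?** The indicator is a response rate for each survey-derived outcome, and the 21-day rule defines who is a non-responder. Numerator and denominator are determined, the criterion is set for that quantity, and nothing elsewhere in the documents conflicts with it. The rate will be what it claims to be. A timely rate is a different quantity, and Table 1 neither claims to measure it nor sets a threshold for it.

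**How far could a timely rate differ?** The documents contain no return times, so the late share has to be assumed, and late itself means nothing until someone chooses a cut-off. Take overall response at exactly 75%, which is 90 of 120:

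- 10% late: 0.75 × 0.90 = 67.5% (81 of 120)
- 20% late: 0.75 × 0.80 = 60.0% (72 of 120)
- 30% late: 0.75 × 0.70 = 52.5% (63 of 120)

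At higher overall response, the timely rate drops below 75% once the late share exceeds:

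- 1 − 0.75/0.80 = 6.3% at 80% response
- 1 − 0.75/0.85 = 11.8% at 85%
- 1 − 0.75/0.90 = 16.7% at 90%

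These figures apply the protocol's 75% to a quantity for which it was not set. The first scenario lies 7.5 points below 75%, inside the 12.7-point margin. The other two, at 15 and 22.5 points, lie outside it only because a larger late share was assumed.

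**How far could the effect estimate move?** Assume a standardized effect of 0.3 that disappears completely in late returns, which is the extreme case. The shift is 0.3 × 0.10 = 0.03 to 0.3 × 0.30 = 0.09. With 90 respondents split evenly, 45 per arm, and no clustering, the 95% half-width is 1.96 × √(2/45) = 0.41. This is optimistic, because there are only six sites. With a t critical value on 4 degrees of freedom (an assumption for comparing two arms of three sites) it is 2.776 × √(2/45) = 0.59, before any intracluster correlation. Even the largest shift, 0.09, is less than a quarter of the smaller half-width (0.09/0.41 = 0.22).

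**The case for a change.** The strongest argument on the other side concerns feasibility. The pilot exists partly to learn whether these outcomes can be collected, and for an outcome set apart by its timing the useful question is how many scores were obtained near the event. A 21-day rate does not answer it. Objective 2 already treats timing as a feasibility matter for the intervention, and objective 3 is already reported by outcome, so an added timely rate for acute stress would cost a sentence or two and a table row. A cut-off chosen after the returns are seen is also weaker evidence than one fixed beforehand.

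Part of this stands. A timely rate would be informative, and none is prespecified. But the step from there to a defect fails for three reasons.

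- **Harm depends on facts the documents do not give.** If the anxiety items refer to the ED visit or the transfer, a late answer is delayed recall of the same event. If they ask about the current state, it describes a later one. The protocol names the instrument but shows neither its items nor its recall period, and does not define the acute period.
- **The information is not lost.** Distribution and completion dates are needed to apply the 21-day rule. The spread of completion times can be described by arm in a descriptive pilot without any cut-off, and the SAP does not prevent it.
- **The stronger remedies are debatable.** Judging acute-stress feasibility on a timely rate would replace the criterion in Table 1 with one that rests on an arbitrary window, and would partly measure how quickly packets are sent. Restricting the analysis to early returns conditions on behaviour after randomization, which may depend on stress or on arm.

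**Conclusion.** The concern does not hold. Its factual basis is correct: the instrument is shared, the return limit is common to all surveys, last acceptance falls on day 21-24, and no analysis by completion date is planned. None of this makes a number, rule or result in the plan wrong. Objective 3 is well defined and will be correctly estimated under the 21-day rule.

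The possible consequence for the acute-stress estimate is a shift of 0.03-0.09 on the standardized scale, against a half-width of 0.41 or more. That rests on an assumed effect of 0.3, its complete loss in late returns, an assumed late share of 10-30%, and 45 respondents per arm. The feasibility scenarios rest on the same unsupported late shares. The outcome is exploratory, its analysis is descriptive, and the SAP states that the pilot is not powered to compare the arms. Describing completion times is a reasonable reporting option, but the plan does not need correction without it.

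### Sites-minus-one degrees of freedom (5 and 2) suit the pooled feasibility proportions only if sites contribute about equally; the SAP should name the interval method and allow for unequal sites

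*Combined protocol and SAP*

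**What the plan says.** The opening paragraph of the Statistical Analysis Plan commits to intervals for all three feasibility objectives: "proportions with 95% CI will be calculated for protocol assignment adherence, fidelity, and survey response rates". On method it says only that "we will use analysis methods for clustered data when estimating confidence intervals, treating ED sites as clusters". It names no variance estimator, no weighting (patients or sites) and no small-sample correction.

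The one further detail is in the SAP's sample-size paragraph, which expects the intervals to be widened by clustering and "by the use of critical values from t-distributions with only 5 or 2 degrees of freedom": 5 df for the six sites of objectives 1 and 3, and 2 df for the three intervention sites of objective 2.

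Three other places bear on how evenly sites will contribute:

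- Table 1, objective 1, defines the indicator as a "Proportion of eligible patients for whom the protocol assignment" is followed, which is a patient-level quantity.
- Eligibility: "All eligible children will be enrolled in the study". No per-site cap is stated.
- Procedures Involved, Randomization: "Transfer volume will be categorized into less than 21, 21-60, and more than 60 annual pediatric transfers" of the relevant kind, and these bands are used to balance the arms.

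**The concern.** With a pooled proportion, each site's weight is its number of patients. A large site pulls the pooled estimate towards its own rate, so its residual shrinks and the usual cluster-robust variance is biased low. That variance also rests on a few dominant residuals, so it behaves as if it had fewer than sites-minus-one degrees of freedom. Both effects vanish when sites are equal and grow as they diverge.

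If both end bands of transfer volume are represented among the six sites, annual volumes differ more than threefold (at least 61 against at most 20). Intervals labelled 95% would then cover less often than that. They are the trial's stated measure of uncertainty for its feasibility results, including the primary one.

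**Working it through.** **Inputs from the documents.** N = 120 over 6 sites (objectives 1 and 3); N = 45 over 3 sites (objective 2); 95% level; df 5 and 2; success threshold 75%.

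**Assumed, because the documents give no figure.** Site sizes; ICC 0.05 (range 0.01-0.10); true rate p = 0.75; one common distribution of site rates (no difference between arms); pooled proportion with a standard cluster-robust variance.

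**The plan's own figures.** The SAP treats the data "as a sample size one half smaller for objectives 1 and 3 and as 60% smaller for objective 2", giving effective sizes 120 × 0.5 = 60 and 45 × 0.4 = 18.

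- 1.96 × √(0.25/60) = 12.65 points (stated 12.7).
- 1.96 × √(0.25/18) = 23.10 points (stated 23.0).

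The margins reproduce to within 0.1 point. They take no account of site-size variation and are not what is questioned here.

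**Size scenarios.** Annual volumes of 15, 15, 40, 40, 90 and 90 (total 290), scaled to 120 patients, give about 6/6/17/17/37/37. A milder case is 10/10/20/20/30/30 and a stronger one 4/6/12/18/30/50.

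**Variance bias.** Let e_g = y_g − n_g·p̂. The standard robust variance is k/(k−1) × Σe_g²/N². Write s_g = n_g(1−ρ) + ρn_g² and S = Σs_g. In units of p(1−p)/N², the true variance is S and E(Σe_g²) = S − 2Σn_g s_g/N + S·Σn_g²/N². At ρ = 0.05:

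- 6/6/17/17/37/37: S = 283.4; E = 283.4 − 146.6 + 66.7 = 203.5; 1.2 × 203.5/283.4 = 86% of the true variance.
- 4/6/12/18/30/50: S = 310; E = 310 − 195.3 + 84.4 = 199.1; 1.2 × 199.1/310 = 77%.
- Equal sites: 1.2 × 195/234 = 100%.

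**Degrees of freedom.** CR2 replaces k/(k−1) by 1/(1 − n_g/N) within the sum. Under working independence the Satterthwaite df is N² / [Σn_g² + Σ_{g≠h} n_g²n_h²/((N−n_g)(N−n_h))].

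- Equal sites: 14,400/(2,400 + 480) = 5.0.
- 6/6/17/17/37/37: 14,400/(3,388 + 979) = 3.3.
- 4/6/12/18/30/50: 14,400/(3,920 + 1,181) = 2.8.

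With equal sites 1/(1 − 1/6) = 6/5, so CR2 reproduces the k−1 robust interval exactly.

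**Coverage.** Beta-binomial simulation, p = 0.75, ICC 0.05, at least 60,000 replicates per setting (Monte Carlo error about 0.1 point):

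| Six sites | Robust SE, t(5) | CR2, Satterthwaite |
|---|---|---|
| Equal (20 each) | about 94% | identical |
| 10/10/20/20/30/30 | about 93% | about 94% |
| 6/6/17/17/37/37 | about 91% | 94-95% |
| 4/6/12/18/30/50 | about 89% | 94-95% |

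Over ICC 0.01-0.10 the last row runs from about 91% to 88% with t(5). Mean half-width at ICC 0.05 rises under CR2 from 13.4 to 16.6 points for 6/6/17/17/37/37, and from about 13 to 18 points for 4/6/12/18/30/50.

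**Objective 2.** At the same p and ICC, the pooled proportion with t(2) covers about 94% (equal), 93% (7/15/23) and 89% (4/12/29). Width is the larger problem. At p = 0.5, with equal sites and no clustering at all, 4.303 × √(0.25/45) = 32.1 points. (That exceeds the stated 23.0, which is a separate matter.) For 4/12/29 at p = 0.75 and ICC 0.05, CR2 has a mean half-width of about 51 points.

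**The case against.** **Unequal sites are inferred.** Volume bands are balancing categories. The documents do not say that both end bands are filled, and they give no site counts. A reader might conclude that sites will be very unequal and the intervals will be too narrow; the text supports only that they may be. With mild inequality the loss against equal sites is about one point. This stands.

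**The criticised estimator is not named.** The shortfall needs the sites-minus-one rule together with an uncorrected robust variance, and the SAP commits only to the first. An unweighted mean of site proportions on the same 5 df covers about 94.6% for 6/6/17/17/37/37. So 5 df is not wrong in itself. But a site mean estimates a site average, not Table 1's patient proportion. What stands is that the interval is under-specified, and that its one stated rule does not fit the natural reading of the indicator when sites are unequal.

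**The success decision.** It is tempting to say the error runs towards declaring success: for 4/6/12/18/30/50 the lower limit exceeds the true rate about 7% of the time, against a nominal 2.5%. Table 1, however, states plain 75% thresholds. The SAP links the intervals to judging the objectives but gives no lower-limit rule. If the point estimate decides, interval width changes nothing. Equal sites already give about 4%, and CR2 still gives 3.7%, so part of the excess is ordinary skewness.

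**Proportion.** This is a pilot that already plans for clustering and uses t rather than normal critical values. That is fair, and it keeps the point modest.

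**Conclusion.** The concern holds in conditional form. The sites-minus-one rule is an upper limit on the usable degrees of freedom for a pooled patient proportion, reached when sites are equal. If site sizes differ markedly and a standard robust variance is used, six-site intervals labelled 95% would cover about 89-91% at p = 0.75 and ICC 0.05, against 94% with equal sites and 93% with mild inequality. The cause is both lost df (about 3 instead of 5) and a variance estimated at 77-86% of its true value.

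These figures rest on assumed site sizes, ICC, true rate and estimator. Inequality is also not the only source of error: at p = 0.85 and ICC 0.10, even equal sites cover only 91.6% (six sites) or 88.9% (three sites). The documents do not support saying that the reported intervals are certain to be too narrow, or that any feasibility decision would change.

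**What to change.** **Objectives 1 and 3.** Keep the pooled patient proportion, and state in the SAP that its 95% CI uses a CR2 cluster-robust standard error with Satterthwaite df computed from the achieved site sizes. Say that 5 and 2 df are upper limits reached with equal sites. This can be fixed before any site counts are known.

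**Objective 2.** Report the pooled proportion with each site's numerator and denominator, and state that a 95% CI from three sites is very wide and its coverage approximate. Do not move to an unweighted site mean: it changes the target, and for 4/12/29 at p = 0.90 and ICC 0.05 it covers 90.2% against 89.9% for the pooled interval on 2 df, which is practically no gain.

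**Cost.** A few lines of SAP text and standard code; no extra data or patients. The downside is wider reported intervals when sites are unequal, as shown in the working.
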